 - Prolonged respiratory insufficiency – PRI (y/n)
 - Stage 2 AKI (y/n)
 - Stage 3 AKI (y/n)
 - Pre- and post-transplant dialysis and whether or not it was discontinued in the hospital

- Time to dialysis discontinuation
- Clavien Dindo – all for 30 day complications
 - 3b (y/n)
 - 4a (y/n)
 - 4b (y/n)
 - 5, ie. Death (y/n)
 - Highest complication grade
 - Any complication greater than or equal to 3b (y/n)
 - Number of 3b or higher complications
- Survival PATIENT – 90 days
 - (y/n) and number of days
- Survival GRAFT – 90 days
 - (y/n) and number of days
- Dialysis – 90 days
- Creatinine at 90 days if not on dialysis
- eGFR at 90 days
- Completed study (y/n)

Statistical Analysis Plan

No comparison (one group)

- All feasibility data
 - Proportion of all patients who tolerated all 6 interventions
 - Proportion of patients who were intubated for all 6 interventions
 - Proportion of patients who were extubated for at least one intervention and tolerated all 6 interventions
 - For extubated patients: number of interventions tolerated while extubated. Break down into those who tolerated all 6 vs those who didn't tolerate all 6.
 - Mean/median pain score for patients receiving an intervention
 - Present as mean/median plus/minus STDEV/IQR for pain scores and number of interventions. Also histograms would be useful for these as the pain scores are likely going to end up being bimodally distributed.
 - Present as proportions with confidence intervals for all others.

Bivariate analyses – categorical data

Chi-squared or Fisher's exact tests.

- Recipient baseline characteristics
 - Gender, beta blockers at transplant (y/n), CCB at transplant (y/n), HCC (y/n) – based on path report, HTN, CAD, Hx of MI, Peripheral vascular disease, Peripheral neuropathy, HIV, Asthma, COPD, PNA, Current smoker, DM, CKD, On dialysis at time of Tx, Pressors (y/n), Hypertonic saline (y/n), Mechanical ventilation (y/n)
- Donor baseline characteristics
 - Gender, Donor receiving glucocorticoids, Donor on sulfonylureas, Pre-recovery biopsy performed (y/n)
- Operative Variables
 - Propofol used for induction (y/n), Veno-venous bypass used (y/n), Piggypack or bicaval, Post-implantation biopsy (y/n)
- POST-operative Variables
 - Propofol for sedation POST-OP (y/n), Reintubated within 7 days (y/n), **Early allograft dysfunction – EAD (y/n), Prolonged respiratory insufficiency – PRI (y/n)**, Pre- and post-transplant dialysis and whether or not it was discontinued in the hospital

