 - Stage 2 AKI (y/n)
 - Stage 3 AKI (y/n)
 - These need to be discussed. The ideal method for comparison would be as an ordinal variable, using a CMH test. However, numbers may end up being low. Alternatively, can analyze as one y/n (ie. Stage 2 or 3 AKI) or using exact chi-squared.
- Clavien Dindo – all for 30 day complications

- 3b (y/n), 4a (y/n), 4b (y/n), 5 ie. Death (y/n)
 - These need to be discussed. We can analyze each individual complication grade using a 2x2 table. Analysis using an ordinal scale doesn't make sense, unless we take only the highest grade, for example.
 - Death also needs to be discussed. Later, we have 90 day mortality data (yes/no) as well as data regarding number of days survived. So we need to decide (a) if we are including death here at all, (b) if we end up analyzing 2x2 tables, is there any point to analyzing 30 day death separately from 90 days, I think no.
- Any complication greater than or equal to 3b (y/n)
- Other data
 - 90 day patient survival (y/n)
 - Can also analyze using Kaplan-Meier estimates
 - Should we consider gathering the data past 90 days? Our protocol does not say we would do this.
 - 90 day graft survival (y/n)
 - Can also analyze using Kaplan-Meier estimates
 - Patient on dialysis at 90 days (y/n)

Chi-squared or Exact Chi-squared tests (categorical variables with more than two levels for the outcome).

- Recipient baseline characteristics
 - Ethnicity, Primary/secondary etiology of cirrhosis,
- Donor baseline characteristics
 - Ethnicity, OPO (local/regional/national), Cause of Death,
- Operative variables
 - Anesthesia type
- POST-operative variables
 - Stage 2 / Stage 3 AKI (see discussion above)
- Clavien-Dindo
 - Complication grades (see discussion above)

Cochran–Mantel–Haenszel test for Ordinal Data

- Stage 2/3 AKI, Complication grades (see discussion above)

Bivariate analyses – Continuous Data

Student's T-Test vs Mann-Whitney U test

- Recipient baseline characteristics

- Hospital Days (#), Post-Transplant Hospital Days (#), Age years, Height, Weight, BMI, Serum creatinine, eGFR, Total Bilirubin, INR, MELD, Days of mechanical ventilation
- Donor baseline characteristics
 - Age years, Height, Weight, BMI, Hospital days, Macrosteatosis, Microsteatosis, DRI
- Operative variables
 - Surgery length (min), CIT (min), WIT (min), Crystalloid (liters), Albumin (liters), RBC (units), FFP (units), Platelets (units), Cryo (units), Other fluid (likely nothing in this field), UOP (liters), EBL (liters)

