 - Macro/microsteatosis if data become available
- POST-op variables
 - ICU LOS (days)
 - POD 0-7 (8 values total)
 - AST, ALT, Total Bilirubin, INR, Creatinine (if not on HD to begin with and if not already in stage III AKI pretransplant)
 - Here, we need to decide how the data will be analyzed. There are three options: day-by-day comparisons, an omnibus test such as a factorial ANOVA (there will be a problem with missing data if we do this), and bivariate longitudinal linear regression (my personal preference, this accounts for correlation between observations within a subject on different days but at the same time uses all the data)
 - Time to extubation
 - Time to dialysis discontinuation
- Clavien-Dindo
 - Number of 3b or higher complications
- Creatinine at 90 days, eGFR at 90 days.

Multivariate regression analysis

- Logistic regression
 - EAD, PRI, Stage 2/3 AKI
- Longitudinal linear regression
 - AST, ALT, Total bilirubin, INR, Creatinine

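### The 90-day dialysis comparison is not split by dialysis at transplant, so new and persisting dialysis are scored alike and the crude difference carries any imbalance in starting status

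*SAP*

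**What the plan says.** The outcome "Patient on dialysis at 90 days (y/n" stands under Other data in the SAP section Bivariate analyses – categorical data. The tests for that block are "Chi-squared or Fisher's exact tests". The list of available data has the outcome as "Dialysis – 90 days". Neither entry restricts, stratifies or adjusts by dialysis status before transplant.

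Starting status is collected. "On dialysis at time of Tx" is among the recipient baseline characteristics, and it is compared between groups in the same categorical block.

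Other entries that bear on the point:

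- A separate post-operative item covers "Pre- and post-transplant dialysis and whether or not it was discontinued in the hospital". The continuous-data section adds the time until dialysis was stopped.
- Logistic regression, under Multivariate regression analysis, is planned for "EAD, PRI, Stage 2/3 AKI". Dialysis at 90 days is not in that list.
- The Cochran-Mantel-Haenszel test is named only for ordinal AKI stage and complication grade.
- The daily post-operative laboratory values include "Creatinine (if not on HD to begin with and if not already in stage III AKI pretransplant", a restriction by renal status before transplant.

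**The concern.** A recipient who arrives on dialysis and is still on it at day 90 has not recovered renal function. A recipient who was off dialysis at transplant and is on it at day 90 has newly lost it. In a feasibility and safety study the second event is the possible safety signal. The planned 2x2 table scores both as yes and cannot tell them apart.

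Starting dialysis is also likely to predict dialysis at 90 days strongly. If one arm happens to hold more recipients already on dialysis, the crude difference includes that imbalance, and none of the listed analyses of this outcome removes it. The effect can run either way: an apparent difference with no RIC effect, or an excess of new dialysis hidden by fewer starters in the same arm.

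**Working it through.** **Inputs.** The SAP states no sample size, allocation ratio, alpha or dialysis rate, so it has no figure to reproduce. All inputs are assumptions: 1:1 arms of 20 or 50; a share *q* = 20-30% on dialysis at transplant; a 90-day dialysis risk *pD* = 30-50% in them and *pN* = 3-5% in the others; two-sided 5%.

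**1. Strength of the baseline variable.** The share of outcome variance explained is q(1−q)(pD−pN)² / [p(1−p)], with p = q·pD + (1−q)·pN.
- Low end (q = 0.20, 30% and 5%): p = 0.10, and 0.16 × 0.0625 / 0.09 = 0.11.
- High end (q = 0.30, 50% and 3%): p = 0.171, and 0.21 × 0.2209 / 0.1418 = 0.33.

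**2. What an imbalance does to the crude difference.** With no RIC effect, the expected difference is (q1 − q2)(pD − pN). Take 15% versus 35% on dialysis at transplant.
- Risks 30% and 5%: 0.15×0.30 + 0.85×0.05 = 8.75%, against 0.35×0.30 + 0.65×0.05 = 13.75%.
- Risks 50% and 3%: 0.15×0.50 + 0.85×0.03 = 10.05%, against 0.35×0.50 + 0.65×0.03 = 19.45%.

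This is a large imbalance. At 50 per arm and q = 0.25 the standard deviation of the difference is √(2×0.25×0.75/50) = 8.7 points, so 20 points is about 2.3 SD.

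**3. Masking.** Take the same shares with risks of 30% and 5%. The arm with 15% on dialysis reaches the other arm's 13.75% if its risk of new dialysis is (0.1375 − 0.15×0.30)/0.85 = 10.9%. In this extreme case the pooled proportions would be equal although new dialysis ran at 10.9% versus 5%.

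**4. False positives with no RIC effect.**
- Averaged over chance allocation at 20 and 50 per arm, the pooled tests keep their level: about 3-5% for chi-squared and 1-3% for Fisher.
- At 50 per arm, an imbalance of 10 points or more, in either direction, occurs in 26-33% of trials. In those trials the rate is about 7-11% for chi-squared and 3-6% for Fisher, against about 5% for the Mantel-Haenszel test stratified by dialysis at transplant.
- At 20 per arm, given the same imbalance, it is about 4-7% for chi-squared and 1-3% for Fisher.

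A single larger imbalance shows the mechanism. With 50 per arm, 11 versus 4 on dialysis at transplant (about 1.96 SD at q = 0.15, a share below the range above) and risks of 50% and 3%, the expected proportions are (11×0.50 + 39×0.03)/50 = 13.3% and (4×0.50 + 46×0.03)/50 = 6.8%. By exact enumeration the false-positive rate is 15.0% for uncorrected Pearson chi-squared and 6.2% for Fisher.

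**5. Power.** For an odds ratio of 0.3, the stratified Mantel-Haenszel test gains about 2-8 percentage points over pooled chi-squared at 50 per arm, and about 0.5-2 points at 20 per arm. These gains are for the large-sample stratified test. An exact version is more conservative, as Fisher's test is relative to chi-squared.

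**The case against.** Under random allocation an unadjusted comparison is valid, and stratifying is a choice about precision and about conditioning on the observed imbalance. That stands. A reader might infer that the planned test inflates type I error overall, or that any chance imbalance will show up as a kidney effect of RIC. The documents do not support this. The SAP does not describe allocation, sample size or rates. On average the pooled tests keep their level. Fisher's test, which the SAP also names, stays near or below 5% even given a 10-point imbalance.

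A reader might also infer that the SAP does nothing to separate new from persisting dialysis. It does something: the pre- and post-transplant dialysis item and the time to stopping address this in hospital. They do not follow the patient to day 90 and do not change the 90-day test.

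The creatinine restriction is weaker evidence than it looks. Creatinine at 90 days is likewise limited to patients not then on dialysis, so the reason may be that creatinine is hard to interpret under dialysis. It need not mean that the authors saw a baseline problem and failed to carry it over.

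The baseline comparison would reveal an imbalance in starting dialysis. It would not correct the 90-day result, and the SAP does not say what would follow. The SAP also states no denominator for this outcome; that all recipients are pooled is read from the absence of any restriction.

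Finally, this is one line among dozens of comparisons in a plan that still marks several items for discussion. That limits the severity but does not remove the point.

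**Conclusion.** The point holds as a matter of interpretation and conditional bias. As planned, the 90-day dialysis result cannot distinguish new dialysis from non-recovery, and its crude difference carries any imbalance in starting status. The first part needs no assumed rate. The size of the second rests wholly on assumed rates and arm sizes. On those assumptions, the conditional false-positive rate is clearly raised only for chi-squared at about 50 per arm, and the power gain from stratifying is small to modest. If allocation was not random, the concern is greater, because an imbalance would no longer be a matter of chance. The severity is minor to moderate.

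**What to change.** In the SAP, compare 90-day dialysis with an exact Cochran-Mantel-Haenszel test stratified by dialysis at transplant, with a common odds ratio or risk difference. Report two rows by arm, each with its own denominator: new dialysis at 90 days among recipients not on dialysis at transplant, and persisting dialysis among those who were. Keep the pooled proportion as description only.

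The cost is a line or two of SAP text and one extra table, since both fields are already collected. The downside is that the stratum on dialysis at transplant may be small, so its own estimate will be imprecise.

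### POD 0-7 creatinine is screened on pre-transplant status only, so values lowered by newly started dialysis stay in and can shrink the between-group difference

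*SAP*

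**What the plan says.** The restriction appears twice in the SAP in the same words, once under Available Data (POST-Operative Variables) and once under Bivariate analyses – Continuous Data (POST-op variables): "Creatinine (if not on HD to begin with and if not already in stage III AKI pretransplant". It belongs to the repeated laboratory series described as "POD 0-7 (8 values total".

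Elsewhere the SAP shows that it expects dialysis after transplant:

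- It records, and compares as a categorical variable, "Pre- and post-transplant dialysis and whether or not it was discontinued in the hospital".
- The data list defines the later value as "Creatinine at 90 days if not on dialysis". The matching analysis line under Continuous Data does not repeat that limit.

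The analysis of the daily values is left open among three options: day-by-day comparisons, a factorial ANOVA, and a longitudinal linear regression. Of the ANOVA the SAP says "there will be a problem with missing data if we do this". It prefers the regression because "this accounts for correlation between observations within a subject on different days but at the same time uses all the data". Creatinine is listed again for longitudinal regression under Multivariate regression analysis, with no dialysis rule or dialysis term. Logistic regression is planned there for "EAD, PRI, Stage 2/3 AKI".

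**The concern.** Both conditions in the restriction describe the patient before transplant. A patient who passes them and starts dialysis on, say, POD 2 still contributes all later creatinine values. Those values reflect dialysis as well as kidney function. The presumable reason for excluding patients already on haemodialysis, that their creatinine no longer measures renal function, applies equally to dialysis begun during the week, but the rule stops at baseline.

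At stake is the reading of this one series. If the arm with worse renal function is dialysed more often, its creatinine is pulled down more often, and harm or benefit in daily creatinine is understated. The gap is the same under all three options, because none of them changes which values are eligible.

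**Working it through.** The SAP has no figure to reproduce: it states no group sizes, dialysis rates, creatinine means or standard deviations. Every number below is an assumption, used to establish direction and a plausible range.

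**Step 1: arm means.** Let p be the share of an arm newly on dialysis, m the mean creatinine of the other patients, and c the mean of the dialysed patients. Then

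arm mean = (1 − p)·m + p·c.

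Assume m = 1.5 mg/dL in arm B and 1.5 + s in arm A, and c = 4.0 if patients needing dialysis were left undialysed. Measured on dialysis, c is 3.0, 2.0 or 1.5. With s = 0 the difference A − B is (pA − pB)·(c − 1.5). For 20% vs 10%:

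- undialysed: 0.10 × 2.5 = 0.250
- measured, c = 2.0: 0.10 × 0.5 = 0.050

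| New dialysis, A vs B | s | Undialysed | c = 3.0 | c = 2.0 | c = 1.5 | Dialysed values deleted |
|---|---|---|---|---|---|---|
| 10% vs 5% | 0 | 0.125 | 0.075 | 0.025 | 0.000 | 0.000 |
| 20% vs 10% | 0 | 0.250 | 0.150 | 0.050 | 0.000 | 0.000 |
| 30% vs 15% | 0 | 0.375 | 0.225 | 0.075 | 0.000 | 0.000 |
| 20% vs 10% | 0.2 | 0.410 | 0.310 | 0.210 | 0.160 | 0.200 |
| 15% vs 15% | 0.2 | 0.170 | 0.170 | 0.170 | 0.170 | 0.200 |

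Unequal rates attenuate the difference; equal rates leave it unchanged. The zeros at c = 1.5 follow from setting c equal to m. The last column shows that deletion alone is no cure, because it removes the worst patients selectively.

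**Step 2: courses over POD 0-7.** Simulation assumptions: 40 per arm, geometric mean 1.3 at POD 0, log-scale SDs of 0.35 (intercept) and 0.12 (residual), and slope SD 0.09 (linear) or 0.13 (peaked). Dialysis follows an observed value above 3.5 or 2.75. That gives 10% vs 22% or 19% vs 35% dialysed (linear), and 12% vs 24% or 23% vs 39% (peak at POD 4). The result is the between-arm difference in log-creatinine slope per day, with dialysed creatinine 1.5 to 2.5. The ranges cover runs with separately chosen arm slopes.

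- Linear courses: true about 0.055, dialysed values kept 0.024 to 0.043. Loss: 1 − 0.043/0.055 = 22% to 1 − 0.024/0.055 = 56%.
- Peak at POD 4: true about 0.031, kept 0.007 to 0.022. Loss: 1 − 0.022/0.031 = 29% to 1 − 0.007/0.031 = 77%.
- Little dialysis (2% vs 5-6%): loss 9% (linear) or 22% (peak at POD 4).
- Dialysis unrelated to creatinine, 5% vs 15%, no true difference: bias 0.005 to 0.006, away from none.

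**Step 3: deletion over the week.** In the linear case the true POD 7 ratio is exp(7 × 0.055) = 1.47. Keeping dialysed values gives 1.25 to 1.32; deleting them and comparing that day alone gives 1.30. With a peak at POD 4 the figures are 1.21 (true), 1.10 to 1.17 (kept) and 1.12 (deleted).

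**The case against.** **The text is unsettled.** The analysis method is still to be decided, and the remark about using all the data answers the ANOVA's missing-data problem. A reader might infer that the SAP has chosen to retain on-dialysis values. It has not; it is silent. The protocol is not at hand and may address this. What remains is that the SAP writes its own eligibility rule for these values, twice, and that rule admits them under any of the three options.

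**Renal harm is visible elsewhere.** A reader might infer that the plan conceals renal harm. The document does not support that: in-hospital dialysis, stage 2 and 3 AKI and dialysis at 90 days are all compared separately. Those comparisons show the events but do not correct the creatinine comparison, which would still be reported.

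**The direction is conditional.** This stands. Attenuation needs dialysis that follows creatinine and differs by arm. A reader might also infer that the sign could reverse. In the simulations that happened clearly only with peaked courses and an assumed dialysed creatinine of 1.0 (−0.004 and −0.009).

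**Creatinine as measured is a legitimate descriptive target** if dialysis is reported beside it. That is fair, but the SAP does not declare this target, and its 90-day data item points the other way. The 90-day rule shows awareness of the problem; as plain deletion it is not a model to copy.

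**An elaborate model may not fit.** An unstructured covariance for 8 days has 8 × 9/2 = 36 parameters, and the SAP itself warns, for AKI, that numbers may be low. This stands, so no single model is insisted on below.

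**Conclusion.** The point holds as a minor one. The restriction looks only at status before transplant, so creatinine lowered by dialysis newly started in POD 0-7 enters both the group comparison and the longitudinal regression. If dialysis follows rising creatinine and is more frequent in one arm, that arm's creatinine looks better than it was. The size cannot be found from the SAP: the assumed settings give a loss from about 9% to most of the difference, and little or none when dialysis rates are equal. The effect is confined to this secondary laboratory series.

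**What to change.** Extend the restriction to dialysis status when creatinine is measured, so that values after the first post-transplant dialysis are not analysed as ordinary values. Then state:

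1. **Main analysis.** A likelihood-based repeated-measures model that keeps each patient's pre-dialysis values, for example with day as a categorical factor and a covariance structure the sample size supports. Do not rely on day-by-day tests after deletion.
2. **Beside it.** A rank analysis in which dialysed days, and days after death, take the worst rank; for example, each patient's mean rank over POD 1-7 compared by Mann-Whitney. Report new dialysis in POD 0-7 by arm.
3. **Values after dialysis is discontinued within the week.** Say how they are treated.
4. **Multivariate longitudinal regression.** Apply the same rule to creatinine there.

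The cost is a few sentences, one derivation rule, one model and one supporting analysis. The data list holds time to dialysis discontinuation but no start day, so the start day must be taken from the chart for the dialysed patients.

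There are two downsides. The model describes creatinine as if dialysis had not begun and assumes that missingness is explained by earlier observed values. In the simulations a categorical-day model recovered the simple cases (0.055 against 0.055 linear, 0.030 against 0.030 for a POD 4 peak at threshold 3.5). It missed when the steepest patients followed a differently shaped course (0.041 against a true 0.062, and 0.061 against 0.048), though by less than keeping the values did (0.020 and 0.031). The rank analysis avoids that extrapolation but counts dialysis begun for other reasons as a bad outcome.

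### The bivariate comparison of the POD 0-7 labs has no chosen method, main model or group contrast, and creatinine after post-transplant dialysis has no analysis rule

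*SAP*

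**What the plan says.** The five labs measured on eight days ("AST, ALT, Total Bilirubin, INR, Creatinine") sit under Bivariate analyses – Continuous Data, POST-op variables. On the method the SAP says: "Here, we need to decide how the data will be analyzed. There are three options: day-by-day comparisons". The second option is an omnibus test such as factorial ANOVA, with the SAP's own caveat that "there will be a problem with missing data if we do this". The third is "bivariate longitudinal linear regression (my personal preference, this accounts for correlation between observations within a subject on different days", which records a preference and not a decision.

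The section Multivariate regression analysis then lists longitudinal linear regression for the same five labs, without hedging. It names no covariates and no contrast.

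Creatinine on POD 0-7 is used "if not on HD to begin with and if not already in stage III AKI pretransplant". Available Data also lists "Pre- and post-transplant dialysis and whether or not it was discontinued in the hospital", and for the later time point "Creatinine at 90 days if not on dialysis". The recipient baseline values in the continuous-data section include "Serum creatinine, eGFR, Total Bilirubin, INR, MELD". No pre-transplant AST or ALT is listed.

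**The concern.** An analysis plan should settle the method before group results are seen. Here the bivariate method is declared open. Taking up the preferred option would still leave two longitudinal analyses of each lab, unranked, with no statement of whether the group effect is a difference in level over the week or in change over days. Either could be chosen once the results are known, and a nominal 5% test would then no longer be a 5% test.

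The creatinine gap is of another kind. Dialysis itself lowers measured creatinine. A patient whose kidneys fail after transplant and who starts dialysis within the week would contribute falling values that the model reads as recovery. If dialysis is more frequent in one group, the comparison is distorted in that group's favour.

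**Working it through.** **No figure to reproduce.** The SAP states no alpha, sample size, SD or power. The error rates below assume two-sided 0.05 and no true effect. The simulated ranges come from 5 labs x 8 days of correlated normal values, 4,000 replicates in each of 36 settings: equal or AR(1) day correlation of 0.5, 0.7 or 0.9; between-lab correlation of 0, 0.3 or 0.6; 20 or 40 per arm.

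**1. What is open and what is fixed.**

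| Item | Bivariate section | Multivariate section |
|---|---|---|
| Method | open among three | longitudinal linear regression |
| Rank (main or supporting) | not stated | not stated |
| Group contrast | not stated | not stated |

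**2. Level or slope chosen afterwards, one lab.** The eight-day mean weights the days symmetrically about mid-week and the linear slope weights them antisymmetrically. Under equal or AR(1) correlation with constant variance the two contrasts are therefore uncorrelated, so the chance that at least one gives p < 0.05 is about 1 − 0.95² = 0.0975. Simulation gives 0.091 to 0.106. One pre-stated contrast gives 0.05.

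**3. Unadjusted or baseline-adjusted chosen afterwards, one lab.** With a baseline correlation r of 0.2 to 0.7, simulation gives 0.056 to 0.092. Adjustment lowers the variance by r²: 0.2² = 4%, 0.5² = 25%. The SAP gives no value of r.

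**4. If day-by-day testing were chosen.** 5 labs x 8 days = 40 tests, and 40 x 0.05 = 2 expected false positives. The expected count does not depend on the correlation (simulated 1.9 to 2.2).

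**5. If the ANOVA needed all eight values.** With values missing independently at an assumed 5% or 10%, the share of complete patients is 0.95⁸ = 66% or 0.90⁸ = 43%.

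**6. What does not come from this gap.** Five labs with one fixed contrast each give 1 − 0.95⁵ = 23% if independent, and 16-23% in simulation. This is ordinary multiplicity. It remains after the choices are fixed.

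**7. Creatinine rules side by side.**

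| Period | Rule in the SAP |
|---|---|
| Before transplant | patients on HD or in stage III AKI are left out of the POD 0-7 analysis |
| POD 0-7, after post-transplant dialysis starts | none |
| 90 days | only if not on dialysis |

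The SAP treats creatinine on dialysis as unusable at both ends and is silent on the week between. The number of patients affected cannot be worked out from it.

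**8. Timing of POD 0.** The SAP lists a POD 0 value for all five labs and six interventions, but does not say whether POD 0 is drawn before or after the first one. POD 0 may therefore be a baseline or an outcome.

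**The case against.** The strongest reply is that the method is not open for the labs as a whole. The multivariate section commits to longitudinal regression for the same five outcomes, so the indecision affects one of two planned analyses. That stands, and the point is limited accordingly.

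Second, large error rates are easily blamed on this gap. A reader might quote the five-lab figure, but step 6 shows that it is ordinary multiplicity. The day-by-day count applies only to an option the SAP's author does not prefer. A reader might also infer a seriously inflated test from a wrong covariance structure. That requires a particular working model, such as a random intercept fitted to serially correlated data, and the SAP names no such model. An unstated covariance structure or convergence fallback is missing detail, not an error.

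Third, a pre-stated unadjusted main model would prevent selective choice just as well as an adjusted one. This is correct. The case for adjustment is possible precision for the three labs with a recorded baseline, and that gain may be small.

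Fourth, it is tempting to say that AST and ALT have no baseline. The SAP supports only that none is listed before transplant; whether POD 0 could serve is unclear.

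Finally, the creatinine gap is narrow, because patients with severe renal failure before transplant are already left out. It is still real, since the SAP's rules on either side show that it regards such values as not comparable.

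**Conclusion.** The point holds in limited form. The SAP itself says that the bivariate POD 0-7 method is undecided. It does not rank the bivariate and multivariate analyses or state a group contrast, and it has no rule for creatinine after post-transplant dialysis begins. Under the assumptions stated (two-sided 0.05, 20-40 per arm, no true effect), leaving level or slope open roughly doubles the error within one lab, from 5% to about 9-11%. Day-by-day testing, if chosen, would bring about 2 expected false positives in 40 tests. The creatinine bias cannot be sized.

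A reader might infer that the trial's main conclusions are at risk. The SAP does not support this: the study is titled a feasibility and safety study, the feasibility data are one-group summaries, and the labs are not labelled primary. What is affected is how the between-group lab results can be read. Severity is SHOULD at most.

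**What to change.** 1. Make longitudinal linear regression the only inferential method for the POD 0-7 labs. Remove day-by-day tests and factorial ANOVA as hypothesis tests, and show daily values with confidence intervals descriptively.
2. State whether POD 0 is before or after the first intervention. Then name one main model and one group contrast per lab. Adjust bilirubin, INR and creatinine for the baseline value already collected. For AST and ALT, use POD 0 as baseline only if it precedes the intervention.
3. Do not analyse creatinine after the start of post-transplant dialysis as ordinary values. Pre-state one analysis rule for both groups (for example, set to missing, with a sensitivity analysis) and report the number affected per group.
4. Label the five lab contrasts exploratory.

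**Cost.** This is mostly SAP wording. Post-transplant dialysis and the three baseline labs are already listed as collected. The SAP does not list a dialysis start date, so its availability should be confirmed.

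**Downsides.** A single contrast such as the weekly mean can dilute a short-lived difference. Missingness after dialysis is informative, hence the sensitivity analysis. The gain from baseline adjustment may be small. The exploratory label does not lower the five-lab error rate; it only tells the reader how to take the results.

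### Adjustment of POD 0-7 total bilirubin, INR and creatinine for the recorded pre-transplant value of the same lab is not pre-specified

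*SAP*

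**What the plan says.** Under Available Data, the recipient baseline list includes serum creatinine, total bilirubin and INR. The post-operative list has the same three labs, with AST and ALT, measured repeatedly: "POD 0-7 (8 values total".

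In Bivariate analyses – Continuous Data, the pre-transplant values ("Serum creatinine, eGFR, Total Bilirubin, INR, MELD, Days of mechanical ventilation") are to be compared between groups by "Student's T-Test vs Mann-Whitney U test". No other direct use of them is written.

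In the same section, under POST-op variables, the repeated labs are "AST, ALT, Total Bilirubin, INR, Creatinine (if not on HD to begin with and if not already in stage III AKI pretransplant"). The method is left open: "There are three options: day-by-day comparisons, an omnibus test such as a factorial ANOVA", and thirdly "bivariate longitudinal linear regression (my personal preference, this accounts for correlation between observations within a subject on different days". The reasons given for preferring the third are within-subject correlation and use of all the data. Starting level is not mentioned.

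The closing section, Multivariate regression analysis, lists longitudinal linear regression for the same five labs and names no covariates.

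**The concern.** A recipient who enters surgery with a very high bilirubin or INR may still show raised values in the first days, whatever the graft is doing. The same holds for creatinine and the kidney. If the comparison ignores the starting value, two things follow. Variation between patients that was present before transplant stays in the error term. And if one group happens to start sicker, part of that difference appears as worse early graft or kidney function.

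Choosing among the three options does not settle this. The preferred option, adopted as written, is a group comparison over time without the baseline value. The multivariate model could supply the adjustment, but with no covariates named, whether it does so would be decided after the data are seen. The study is titled as one of feasibility and safety, and the SAP itself warns of low numbers when it discusses AKI stages, so precision is worth protecting.

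**Working it through.** **Which labs are affected**

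| Lab | Pre-transplant value listed | POD 0-7 outcome | Baseline named in any model |
|---|---|---|---|
| Total bilirubin | yes | yes | no |
| INR | yes | yes | no |
| Creatinine | yes | yes (restricted by pre-transplant HD and stage III AKI) | no |
| AST, ALT | no | yes | not applicable |

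**Inputs.** The SAP gives no sample size, standard deviation, effect, alpha, power or baseline-to-outcome correlation, so there is no stated figure to reproduce. Everything below rests on assumed values. Let r be the correlation between the pre-transplant value and the post-operative value of the same lab.

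**1. Single day.** Adjusted variance = (1 − r²) × unadjusted variance, so the unadjusted standard error is larger by the factor 1/√(1 − r²). A baseline difference of d SD between groups shifts the unadjusted outcome difference by r × d SD.

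| r | Variance removed, r² | SE ratio, unadjusted/adjusted | Shift if d = 0.3 SD |
|---|---|---|---|
| 0.1 | 1% | 1.005 | 0.03 SD |
| 0.2 | 4% | 1.021 | 0.06 SD |
| 0.3 | 9% | 1.048 | 0.09 SD |
| 0.5 | 25% | 1.155 | 0.15 SD |
| 0.7 | 49% | 1.400 | 0.21 SD |

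The formula ignores the small cost of estimating the baseline coefficient. In a small study, the net gain at r = 0.1 may therefore be nil.

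**2. Mean of the eight days.** Assume equal correlation w between any two days and the same r on every day. Unadjusted variance is (1 + 7w)/8; adjusted variance is (1 + 7w)/8 − r².

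- w = 0.5: unadjusted (1 + 3.5)/8 = 0.5625. At r = 0.3, adjusted 0.4725, SE ratio √(0.5625/0.4725) = 1.09. At r = 0.5, adjusted 0.3125, SE ratio 1.34.
- w = 0.8: unadjusted (1 + 5.6)/8 = 0.825. At r = 0.3, adjusted 0.735, SE ratio 1.06. At r = 0.5, adjusted 0.575, SE ratio 1.20.

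So the unadjusted standard error is 6-9% larger at r = 0.3 and 20-34% larger at r = 0.5. If r fades over the week, these figures are too high.

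**3. Power, for illustration only.** Assume 40 per group, a 0.6 SD effect on a single day and two-sided alpha 0.05. Power ≈ Φ(0.6/√((1 − r²) × 2/40) − 1.96). Results: 0.77 unadjusted; 0.80 adjusted at r = 0.3; 0.87 at r = 0.5; 0.96 at r = 0.7.

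**4. Is the unadjusted test invalid?** In a simulation of 5,000 trials per setting, with 40 per group, random allocation and no true effect, the unadjusted t-test rejected in 4.8% (r = 0.3) and 4.9% (r = 0.5), which is nominal. Among the runs whose baseline means differed by more than 0.3 SD (886 and 906 runs), it rejected in 6.5% and 11.3%. With 40 per group, the standard deviation of the chance imbalance is √(2/40) = 0.22 SD, so a difference above 0.3 SD is not rare.

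**The case against.** The strongest reply is that an adjusted analysis of these very labs is planned. An unadjusted step followed by a multivariate step is a coherent sequence, and the SAP does not say which of the two is the main comparison. This stands in part. A reader might infer that the plan rules out baseline adjustment; it does not. What it lacks is any commitment to it.

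A reader might also infer that the comparison is biased. The SAP does not support that. It does not describe allocation, and under randomisation the unadjusted test keeps its overall error rate, as the simulation shows. The shift in the table depends on an imbalance having occurred.

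The gain may also be small. If post-transplant bilirubin and INR mainly reflect the new graft, r will be low and will fall over the week. Plasma given in theatre, which the SAP records, could weaken the INR link further. This stands, and it is why no single figure is offered.

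For creatinine, the SAP already leaves out patients on dialysis or in stage III AKI before transplant, which removes the most extreme starting values. That is a partial safeguard. Variation among those kept is not adjusted for, and bilirubin and INR have no such restriction.

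Finally, these labs are a few among many comparisons and the SAP does not mark them as primary, so the consequence is modest. A protocol might name covariates, but this SAP takes up the choice of model for these labs directly, so it is the natural place to name them.

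**Conclusion.** The point holds as a gap in pre-specification with a readily available better method, and it is a minor one. For total bilirubin, INR and creatinine, every option offered for the POD 0-7 group comparison is unadjusted as written, and the multivariate model does not commit to the recorded pre-transplant value.

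The size cannot be fixed from the SAP. For a single day, the unadjusted standard error is about 0.5-5% larger at r = 0.1-0.3 and 15-40% larger at r = 0.5-0.7; these correlations are assumptions, and the lower range is plausible for bilirubin and INR later in the week. If allocation was random, the cost is lost precision and exposure to chance imbalance. Confounding would follow only if it was not.

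**What to change.** In the longitudinal model for total bilirubin, INR and creatinine, pre-specify the pre-transplant value of the same lab as a covariate, alongside group, day and group-by-day. Name this model as the main group comparison and keep the group-only model as a sensitivity analysis. Use the pre-transplant value and not POD 0, which is on the outcome list. Keep the existing creatinine restriction. State that AST and ALT are analysed without this covariate because no pre-transplant value is listed for them.

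A baseline-by-day term, which lets the influence of the starting value fade, is optional. With eight categorical days it adds 8 − 1 = 7 parameters per lab beyond the baseline term itself, which is a lot if numbers are low. A version linear in day adds one.

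The cost is a few lines of SAP wording and one parameter per lab for the core change. The values are already collected. Patients without a recorded pre-transplant value would need a stated rule.
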